1. Patients with a primary discharge diagnosis of DRG 087 or DRG 088 but clearly judged by the clinical investigator to be due to other causes, i.e. patients presenting to the hospital with symptoms of AECOPD but due mainly to other conditions (pulmonary embolism, pneumonia, pneumothorax, anemia, acute kidney failure, decompensated heart failure, acute ischemic heart disease, new onset atrial fibrillation, stroke, etc.)
2. Patients who required invasive mechanical ventilation during hospitalization
3. Patients with Asthma as primary and principal diagnosis
4. Patients with severe cardiovascular (CV) disease who in the opinion of the investigator are unlikely to survive the 15 month study period
5. Patients considered unable to comply with the study procedures and follow-up in the opinion of the investigator (eg, evidence of alcohol or drug abuse, psychiatric disorder, physical disability, social or geographical obstacles)
6. Patients in whom spirometry is contraindicated (eg, hemoptysis, detached retina, active tuberculosis, last trimester of pregnancy)
7. Patients with other mechanical or overt causes of respiratory symptoms, particularly dyspnea (such as pneumothorax, chest wall trauma, lung fibrosis, lung cancer, anemia, severe obesity (BMI >40) or cachexia (BMI <18))
8. Patients with any major disease which in the opinion of the investigator would prevent study participation, such as dementia, end-stage disease, cachexia, chronically bedridden patient and life expectancy <15 months.
9. Participation in any other interventional study within the last 3 months or concurrent participation in an observational clinical study.

Number of Participants:

The aim is to randomize 464 participants to each intervention group

Adjusting for an expected 10% dropout rate, a total of 516 patients per group will need to be randomized.

The study will be performed at 39 centers in Italy.

Intervention Groups and Duration:

In this study patients will be randomised to receive one of the following two treatment regimens for up to 12 months:

- 1) Usual and optimized treatment for concomitant cardiovascular (CV) diseases plus inhaled long acting bronchodilator(s) (LABD(s))

2) Usual and optimized treatment for concomitant CV diseases plus inhaled long acting bronchodilator(s) and inhaled glucocorticosteroids (ICS).

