4.5 Pooling of sites

Not foreseen.

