Time to first re-hospitalization and/or death will be analysed using the Kaplan-Meier estimator. The number of re-hospitalization and/or death-free patients at the beginning of the period, the cumulative number of patients with re-hospitalization and/or death at the end of the period and the probability of being re-hospitalization and/or death-free at the end of the period with the associate 95% CIs will be presented by treatment for the following study periods: (0-12] weeks, (12-24] weeks, (24-36] weeks and (36 weeks-EoT]. The point estimates and the relative 95% CIs will be

Forms			
Title	Statistical Analysis Plan Template		
Code	Version	Effective Date	Page
FRM_ST03_032	02	02 Oct 2017	18 of 26

presented by treatment for the 75th, 50th and 25th percentiles. Comparison between treatments will be performed using the log-rank test stratified by center.

The LABD(s)+ICS group will be declared to prolong time to first re-hospitalization and/or death, compared to the LABD(s) group, if the difference between the two treatments is significantly in favour of LABD(s)+ICS (i.e., the p-value from the log-rank test is ≤ 0.050).

Plots of first re-hospitalization and/or death-free survival by treatment will also be presented.

The following SAS[®] code will be used to provide the Kaplan-Meier estimates for time to first re-hospitalization and/or death:

```
proc lifetest data=dataset TIMELIST=(12 24 36 EOT_A, EOT_B);
time TIME*EVENT(1);
strata CENTER / group=TMT;
run;
```

where TIME represents the time to first re-hospitalization and/or death or time to censoring, EVENT the censoring indicator (1 = censored patient), CENTER the center and TMT the treatment group; EOT_A, EOT_B, have to be replaced by the last time to first re-hospitalization and/or death or last time before EOT for each treatment group (if any).

Time to first re-hospitalization and/or death will also be analyzed using a Cox proportional hazards regression analysis with center and treatment group as qualitative independent variables and age as quantitative independent variables. The inclusion of any other potential confounding factors in the model will be evaluated during the Data Review, verifying the homogeneity of factors distributions among treatment groups.

The number of patients and the number of patients considered in the model will be provided by treatment. P-values of the independent variables based on Wald chi-square test will also be presented.

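### SAP 7.1 asks for Kaplan-Meier results by treatment, but the only code given for them estimates within each centre-by-arm cell (minor; test and hazard ratio unaffected)

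*SAP*

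**What the plan says.** SAP 7.1 sets out the Kaplan-Meier output for the primary endpoint arm by arm:

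- The counts and event-free probabilities, with 95% confidence intervals, "will be presented by treatment for the following study periods" (cut at 12, 24 and 36 weeks and end of treatment).
- The survival percentiles are "presented by treatment for the 75th, 50th and 25th percentiles".
- "Plots of first re-hospitalization and/or death-free survival by treatment will also be presented". Protocol 9.4.6 likewise asks for a Kaplan-Meier plot by treatment group.

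The same section specifies a log-rank test stratified by centre as the treatment comparison.

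One `PROC LIFETEST` block follows. The SAP introduces it by saying that this "code will be used to provide the Kaplan-Meier estimates for time to first re-hospitalization and/or death". Its stratification statement is "strata CENTER / group=TMT", and the legend makes "CENTER the center and TMT the treatment group". No second `PROC LIFETEST` call appears anywhere in the SAP. SAP 4.5 plans no pooling of sites, so each centre remains its own stratum. The protocol synopsis gives the number of centres: "The study will be performed at 39 centers in Italy".

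**The concern.** In this procedure, a variable named in `STRATA` together with a `GROUP=` variable asks for treatments to be compared within strata. That is what a centre-stratified log-rank test needs. The product-limit estimates, quartiles and `TIMELIST` rows, however, are then computed separately for every combination of the two variables. The call named as the source of the Kaplan-Meier estimates therefore does not produce the estimates that the text requires.

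What is at stake is the descriptive display of the primary endpoint: the by-arm event-free probabilities, the percentiles and the plot. SAP 7.1 repeats the same analyses on the crossover-censored dataset and in the triple-therapy subgroup, so the conflict carries over to both. SAP section 1 requires deviations from the SAP to be explained in the study report. As written, the programmer has to depart from either the text or the code.

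**Working it through.** **Inputs.** 39 planned centres (protocol synopsis); two arms; 464 per arm, or 516 after allowing for 10% dropout; expected event proportions 15% (LABD) and 9% (LABD+ICS) (SAP 3.3); no pooling of sites (SAP 4.5).

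**The plan's own figures.** 464 / 0.90 = 515.6, which rounds up to 516 as stated. The hazard ratio implied by 15% and 9% is ln(0.91)/ln(0.85) = 0.580. For 80% power at two-sided 5%, Freedman's formula gives 112 events. At a mean event proportion of 12% that is 112 / 0.12 / 2 = 467 per arm. A two-proportion calculation without continuity correction gives 460. The stated 464 lies between them, so the sizes and rates used below are consistent with each other.

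**Text and code side by side.**

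| | Text of SAP 7.1 | Code block in SAP 7.1 |
|---|---|---|
| Unit of estimation | treatment arm | centre-by-arm cell |
| Number of curves | 2 | up to 39 × 2 = 78 |
| Treatment comparison | log-rank stratified by centre | log-rank stratified by centre |

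The two agree on the test and disagree on the estimates.

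**Size of a cell, assuming centres of equal size.**

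| | 464 per arm | 516 per arm |
|---|---|---|
| Patients per cell | 464/39 = 11.9 | 516/39 = 13.2 |
| Expected events, LABD | 11.9 × 0.15 = 1.8 | 13.2 × 0.15 = 2.0 |
| Expected events, LABD+ICS | 11.9 × 0.09 = 1.1 | 13.2 × 0.09 = 1.2 |
| Chance of no event, LABD | 0.85^11.9 = 14% | 0.85^13.2 = 12% |
| Chance of no event, LABD+ICS | 0.91^11.9 = 33% | 0.91^13.2 = 29% |

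The 516 column applies the full event proportions to everyone randomized, including expected dropouts, so the two columns are best read as a range. One simulated trial of 928 patients, spread almost evenly over 39 centres, gave 78 curves, of which 18 had no event.

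**With treatment as the only stratum.** There would be two curves of about 464 patients each, with 464 × 0.15 = 70 and 464 × 0.09 = 42 expected events.

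**The case against.** The strongest reply is that the specification is right and only a code sketch is incomplete. The text states three times that the output is by treatment. The end-of-treatment placeholders in the code are defined for each treatment group, so two-arm output is plainly intended. SAP section 1 describes the document as general guidelines, and nothing in it says that code overrides text. The block is also a template. Its `EOT_A` and `EOT_B` entries must be replaced by data values before it can run, and the neighbouring Cox block uses `TRT` where its legend defines `TMT`. Dozens of curves labelled by centre would be noticed at the first run.

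Most of this stands, and it is why the point is minor. It does not remove the contradiction: the SAP prescribes this block for these estimates and gives no other call.

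Three stronger readings are tempting, and the documents do not support them:

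- A reader might infer that the primary result is at risk. It is not. The success criterion is the log-rank p-value, for which the code is correct, and the hazard ratio comes from a separate procedure.
- A reader might infer that wrong arm-level numbers would pass silently into the report. The output would be visibly per centre, and there is no evident route by which it would be taken for an arm-level result.
- A reader might infer that the Kaplan-Meier probabilities are the only absolute result planned for the primary endpoint. The same table also calls for by-arm counts of patients still event-free and cumulative counts of patients with events.

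**Conclusion.** The inconsistency is real and minor. The call prescribed for the Kaplan-Meier estimates cannot supply the by-arm probabilities, confidence intervals, percentiles and plots that SAP 7.1 requires. It would give up to 78 centre-by-arm curves instead of two arm-level curves. No planned test, p-value or hazard ratio changes.

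The conclusion rests on three assumptions. First, the behaviour of the named procedure is general knowledge of the software; the documents show no output. Second, 78 is an upper figure that needs all 39 planned centres to enrol into both arms; empty or single-arm centres lower it. Third, the 12 to 13 patients per cell and the event figures assume equal-sized centres and the design event proportions. They show how thin the cells would be. They do not measure bias in a planned result, since no centre-level curve is meant to be reported.

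**What to change.** Separate estimation from testing in SAP 7.1:

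1. Add a `PROC LIFETEST` call with `strata TMT` and the `TIMELIST` option, and name it as the source of the by-arm event-free probabilities, confidence intervals, percentiles and plots.
2. Keep the call with "strata CENTER / group=TMT", labelled as the source of the centre-stratified log-rank p-value only.
3. State that both calls apply to the crossover sensitivity analysis and the triple-therapy subgroup.

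The cost is one extra procedure call and a sentence of SAP text. The estimand, sample size and decision rule do not change.

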9.4.8. Other Analyses

A subgroup analysis will be performed by considering the patients randomized with Triple Therapy (LAMA+LABA+ICS) or LAMA+LABA. The analysis of primary endpoint and the number of re-hospitalizations and deaths (all cause) secondary analysis will be performed on this subset of patients.

Other subgroup analyses may be performed for efficacy and safety endpoints based on baseline disease characteristics which could provide evidence to assess effectiveness, adherence levels and the true value of adding ICS treatment to LABD.

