3.1 General design and plan

 cros nt	Forms			
	Title Statistical Analysis Plan Template			
	Code	Version	Effective Date	Page
	FRM_ST03_032	02	02 Oct 2017	8 of 26

This will be a phase IV, open label, multicenter, randomized pragmatic study in frail elderly patients with COPD. Participants will be treated with either inhaled LABD alone or LABD combined with inhaled glucocorticosteroids. The choice of the specific LABD and ICS to be used will be left to the discretion of the clinical investigator. Thus, the proposed study will be a real-life but randomized study with a 12-month treatment period followed by 3 months follow-up. The center will be considered as a unique stratifying factor, so the study will have a balanced-block center-stratified design.

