3.3 Sample size justification

The sample size calculation is based on the superiority criteria of the LABD+ICS group versus LABD alone group in terms of re-hospitalization and/or death. With 464 patients in each group, the percentage of patients experiencing the composite event (re-hospitalization and/or death) is expected to be 9% in the LABD+ICS group and 15% in the LABD alone group. A log-rank test (two-sided 5% significance level) will have 80% power to detect a difference between treatment groups in terms of time to first re-hospitalization and/or death (primary efficacy endpoint). Adjusting for an expected 10% dropout rate, a total of 516 patients per group will need to be randomized.

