4.3 Sub-group analyses

The following subgroup will be defined:

Forms			
Title		Statistical Analysis Plan Template	
Code		Version	Effective Date
FRM_ST03_032		02	02 Oct 2017
		12 of 26	

- Patients treated with triple therapy: subjects who were treated with “LAMA+LABA” or “LAMA+LABA+ICS”. Considering that LABD category of treatments can be subdivided in “LAMA”, “LABA” or “LABA+LAMA”, this subgroup will be selected. Other subgroup analyses may be performed during post-hoc analyses for efficacy and safety endpoints based on baseline disease characteristics which could provide evidence to assess effectiveness, adherence levels and the true value of adding ICS treatment to LABD.

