Treatment effect will be presented as a hazard ratio with the associated 95% Wald CI and p-value.

The following SAS[®] code will be used to estimate the Cox proportional hazards regression model:

```
proc phreg data=dataset;
class CENTER TRT;
model TIME*EVENT(1) = CENTER TRT AGE / ties=exact;
hazardratio TRT / cl=wald;
run;
```

where TIME represents the time to first re-hospitalization and/or death or time to censoring, EVENT the censoring indicator (1 = censored patient), TMT the treatment group, CENTER the center and AGE the age.

The variable TMT will be ordered in SAS in the following order:

- 1 = LABD;
- 2 = LABD + ICS.

Forms			
Title	Statistical Analysis Plan Template		
Code	Version	Effective Date	Page
FRM_ST03_032	02	02 Oct 2017	19 of 26

If the option “ties=exact” requires a considerable amount of computer resources, the Efron approximation will be used (“ties=efron”).

A sensitivity analysis will also be carried out excluding efficacy data (i.e., hospitalization and death) collected after the crossover occurrence date. The same analyses described above will be repeated on this modified dataset.

Finally, the same analyses described above will be repeated in the subgroup of patients treated with triple therapy.

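### The LAMA+LABA subgroup is analysed alone, with no interaction estimate and no single-bronchodilator result, and its protocol-planned count analysis is missing from the SAP without being declared

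*SAP*

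**What the plan says.** Protocol 9.4.8 names one subgroup, patients randomized with triple therapy or with LAMA+LABA, and specifies two analyses in it: "The analysis of primary endpoint and the number of re-hospitalizations and deaths (all cause) secondary analysis will be performed on this subset of patients".

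SAP 4.3 defines the same subgroup by the treatment patients received. It introduces the selection with "Considering that LABD category of treatments can be subdivided in", lists LAMA, LABA and the combination, and selects the combination only. Any other subgroup is left to post-hoc work.

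SAP 7.1 sets out the Kaplan-Meier estimates, the log-rank test with its 0.050 criterion, and a Cox model with centre, treatment and age. Its last paragraph reads "Finally, the same analyses described above will be repeated in the subgroup of patients treated with triple therapy". Neither this Cox model nor the Poisson model in SAP 7.2 has a regimen term or an interaction.

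SAP 7.2 places the count analyses on the ITT population and does not mention the subgroup. SAP 4.8 lists two departures from the protocol: dropping the paired t-test p-values, and listing vital signs and physical examination only. SAP 4.1 applies the p ≤ 0.05 convention to all inferential analyses, and protocol 9.4.5 plans no multiplicity adjustment.

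**The concern.** A test inside one subset addresses whether there is an effect there. It does not address whether the effect is different there. With no interaction term and no estimate for single-bronchodilator patients, the report gives the reader two results to compare: the overall one and the subset one. If the first is significant and the second is not, the natural reading is that ICS adds nothing on top of dual bronchodilation. Yet the smaller number of events in the subset can produce that pattern when the effect is identical in everyone. Nothing in the SAP labels the subset p-value as descriptive.

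The second issue needs no modelling. An analysis the protocol says will be done has disappeared from the SAP, and the section that exists to record such changes is silent.

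**Working it through.** **Inputs.** From SAP 3.3: "With 464 patients in each group", the composite event "is expected to be 9% in the LABD+ICS group and 15% in the LABD alone group", and "A log-rank test (two-sided 5% significance level) will have 80% power to detect a difference between treatment groups". Also from SAP 3.3: "Adjusting for an expected 10% dropout rate, a total of 516 patients per group will need to be randomized". The share f of patients on LAMA+LABA is not given, because the investigator chooses the regimen. I assume 30%, 50%, 70% and 90%, with the same hazard ratio and event rates in both parts.

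**1. The plan's own figure.**
- HR = ln(0.91)/ln(0.85) = 0.580.
- Freedman events = (1.960 + 0.842)² × [(1 + HR)/(1 − HR)]² = 111.3.
- Per arm = 111.3/(0.15 + 0.09) = 464, and 464/0.90 = 515.6, so 516. Both stated figures reproduce.
- Schoenfeld's formula gives 107 events and 82% power at 464 per arm. I use the stated 80%, so the expected overall Z is θ = 1.960 + 0.842 = 2.802.

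**2. Power inside the subset.** Its expected Z is θ√f, so power = Φ(2.802√f − 1.960). At f = 0.5 this is Φ(1.981 − 1.960) = 0.508.

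**3. Overall versus subset.** Write Z(overall) = √f·Z(subset) + √(1−f)·Z(remainder), with the two parts independent, unit variance and means θ√f and θ√(1−f). Two million simulated draws gave the last two columns.

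| Assumed share f | Subset power | Overall significant, subset not | Subset not significant, given overall significant |
|---|---|---|---|
| 30% | 34% | 48% | 60% |
| 50% | 51% | 31% | 39% |
| 70% | 65% | 17% | 22% |
| 90% | 76% | 6% | 8% |

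The reverse pattern (subset significant, overall not) occurs in about 2% of trials at each of these shares.

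**4. Interaction test.** The contrast √(1−f)·Z(subset) − √f·Z(remainder) has mean θ[√(1−f)·√f − √f·√(1−f)] = 0 and variance 1 under a common hazard ratio. It therefore rejects 5% of the time at any share.

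**5. Precision of the interaction.** Approximate variance of the log ratio of hazard ratios = (4/111.3) × [1/f + 1/(1−f)]. At f = 0.5 this is 0.0359 × 4 = 0.144, so SE = 0.379 and the 95% interval runs from the estimate divided by exp(1.96 × 0.379) = 2.10 to the estimate multiplied by 2.10. At 30% or 70% the variance is 0.0359 × 4.76 = 0.171, SE = 0.414, and the factor is 2.25.

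**6. The count analysis.** Protocol 9.4.8 names two analyses for the subset. The repeat clause in SAP 7.1 refers to analyses described above it and closes the primary-endpoint section. The Poisson model first appears afterwards, in SAP 7.2, so the clause cannot cover it. Neither item in SAP 4.8 concerns it.

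**The case against.** The within-subset hazard ratio and its confidence interval directly estimate triple therapy against LAMA+LABA, a comparison the protocol's introduction discusses. Whether the effect differs by regimen is a further question that neither document lists as an objective. The ITT is the primary analysis set, the protocol files the subgroup under other analyses, and SAP 7.1 will report estimates with intervals as well as p-values. This stands. It is why the planned subset estimate should be kept, and why the interaction is an addition rather than a replacement.

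An interaction on regimen may also mislead. The trial is open-label, the investigator chooses the regimen, and "The center will be considered as a unique stratifying factor, so the study will have a balanced-block center-stratified design", so regimen is not a stratum. If it is chosen once the arm is known, membership can depend on the arm. The SAP's definition by treatment received widens that risk compared with the protocol's definition by randomization. This also stands and shapes the fix.

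Two stronger readings are tempting. A reader might infer that a uniform effect would look subgroup-specific about half the time. That figure is the chance that subset and remainder fall on opposite sides of 0.05 (55%, 50% and 55% at shares of 30%, 50% and 70%). The SAP plans no test in the remainder, so that pair of p-values will not exist. Even if it did, only 12%, 25% and 43% would point to the named subgroup alone. A reader might also infer that an efficacy claim will rest on the subset p-value. The general 0.05 convention and the repeated criterion permit that reading, but no section states such a claim.

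**Conclusion.** The concern holds in two parts. First, the planned subset analysis cannot show whether the ICS effect depends on bronchodilator regimen. Under a uniform effect, the contrast a reader will see (overall significant, subset not) arises in about 48%, 31% and 17% of trials at shares of 30%, 50% and 70%. It is material unless nearly everyone is on dual bronchodilation; at 90% it is about 6%. These figures rest on the assumed shares, the design hazard ratio of 0.58, equal event rates in both parts, and a normal approximation that ignores centre stratification.

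Second, the SAP drops the subset count analysis in protocol 9.4.8 without declaring it. This rests on the text alone. Neither part affects the validity of the primary ITT test.

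**What to change.** - **SAP 7.1:** keep the subset hazard ratio and interval. Add to the ITT Cox model, with its present terms, LABD regimen (LAMA+LABA or single LABD) and its interaction with treatment. Report the hazard ratio with 95% CI for both regimen groups and the interaction estimate with 95% CI. The model does not need to change to centre stratification.
- **SAP 4.3:** define regimen as that assigned at randomization, in line with the protocol, rather than as received. Tabulate it by arm, and note that it may still depend on arm if chosen after allocation was known; an interaction term does not repair that. State that within-subgroup p-values are descriptive.
- **SAP 7.2 or 4.8:** add the count analysis in the same form (regimen and its interaction with treatment in the Poisson model), or declare and justify its removal.

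The cost is SAP wording and one regimen factor with its interaction in each of two models. No planned analysis is lost. The downside is low power for the interaction: by the working above, its 95% interval spans roughly a factor of 2.1 to 2.25 either side of the estimate. That width is a fair statement of what the trial can say about regimen.
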